Appendix D Acceptable Birth Control Methods

Patients and their partners, who are sexually active and of childbearing potential, must agree to the use of highly effective forms of contraception [as listed below], throughout the period of study treatment or they must totally/truly abstain from any form of sexual intercourse (see below), when this is in line with their preferred and usual lifestyle. Patients on savolitinib must continue contraception for at least 1 month (female patients) and 6 months (male patients) after their last dose.

Acceptable Non-hormonal birth control methods include:

- Total sexual abstinence (when this is in line with the preferred and usual lifestyle). Abstinence must continue for the total duration of study treatment and for at least 1 month after the last dose of savolitinib for females and for at least 6 months after the last dose of savolitinib for males. Periodic abstinence (eg, calendar ovulation, sympto-thermal post ovulation methods) and withdrawal are not acceptable methods of contraception.
- Vasectomised sexual partner PLUS male condom. With participant assurance that partner received post-vasectomy confirmation of azoospermia.
- Tubal occlusion PLUS male condom with spermicide.
- Intra-uterine device (IUD) PLUS male condom with spermicide. Provided coils are copper-banded.
- Acceptable hormonal methods:
- Normal and low dose combined oral pills PLUS male condom with spermicide.
- Etonogestrel implants (eg, Implanon, Norplan) PLUS male condom with spermicide.
- Norelgestromin / Ethinyl Estradiol (EE) transdermal system PLUS male condom with spermicide.
- Intravaginal device (eg, EE and etonogestrel) PLUS male condom with spermicide.
- Cerazette (desogestrel) PLUS male condom with spermicide. Cerazette is currently the only highly efficacious progesterone based pill.
- Intrauterine system [IUS] device (eg, levonorgestrel releasing IUS - Mirena[®]) PLUS male condom with spermicide.
- Hormonal shot or injection (eg, Depo-Provera) PLUS male condom with spermicide.

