 - 11 Adequate coagulation parameters defined as International Normalisation Ratio (INR) and activated partial thromboplastin time (aPTT) < 1.5 x ULN, unless patients are receiving therapeutic anti-coagulation which affects these parameters.
 - 12 Adequate cardiac function defined as an ejection fraction (EF) of $\geq 50\%$.
 - 13 Patients with known tumour thrombus or deep vein thrombosis (DVT) are eligible if clinically stable on anticoagulation for ≥ 2 weeks.
 - 14 Females should be using adequate contraceptive measures, should not be breast feeding, and must have a negative pregnancy test if of childbearing potential, or must have evidence of non-childbearing potential by fulfilling one of the following criteria:

- Post-menopausal defined as aged more than 50 years and amenorrhoeic for at least 12 months following cessation of all exogenous hormonal treatments
 - Documentation of irreversible surgical sterilisation by hysterectomy, bilateral oophorectomy or bilateral salpingectomy but not tubal ligation.
 - Women under the age of 50 years would be considered postmenopausal if they have been amenorrhoeic for 12 months or more following cessation of exogenous hormonal treatments and with LH and FSH levels in the post-menopausal range for the institution.
- 15 Male patients with female partners of child-bearing potential should be willing to use barrier contraception, ie, condoms, during the study and for 6 months following discontinuation of study drug.
- 16 Ability to swallow and retain oral medications.
- 17 Willingness and ability to comply with study and follow-up procedures*.

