3.6 Restrictions

3.6.1 Need for contraception

There are no studies in pregnant women taking savolitinib or sunitinib. However, studies in animals have shown that either drug may cause harm to a foetus. Patients of child bearing potential and their partners who are sexually active, must agree to the use of highly effective forms of contraception while taking study medication. Female patients on savolitinib must continue to use contraception for 1 month after their last dose. Acceptable methods of contraception include full abstinence, tubal ligation, combined oral, transdermal or intra-vaginal hormonal contraceptives, medroxyprogesterone injections (eg, Depo-Provera), copper-banded intra-uterine devices, hormone impregnated intra-uterine systems, and vasectomised partners. All methods of contraception (with the exception of total abstinence) should be used in combination with the use of a condom by their male sexual partner for intercourse.

Studies in animals taking savolitinib have shown some abnormalities in sperm development. Therefore, male patients must use a condom during sexual intercourse with a female partner of childbearing potential (pregnant or not) and refrain from donating sperm during the study and for 6 months after their last dose. For details refer to Appendix D “Acceptable Birth Control Methods”.

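### The protocol gives foetal harm as a reason for contraception with either drug, but sets a post-dose contraception period for women on savolitinib only

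*Protocol*

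**What the plan says.** Section 3.6.1 opens with a reason that covers both arms: "studies in animals have shown that either drug may cause harm to a foetus". It answers with a rule that also covers both arms: sexually active patients of child-bearing potential and their partners "must agree to the use of highly effective forms of contraception while taking study medication".

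For the time after treatment, the women's rule names one drug: "Female patients on savolitinib must continue to use contraception for 1 month after their last dose". Appendix D repeats this in its lead sentence, "Patients on savolitinib must continue contraception for at least 1 month (female patients) and 6 months (male patients) after their last dose", and again in the bullet on abstinence, which for women runs "for at least 1 month after the last dose of savolitinib for females".

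Inclusion criterion 14 in section 3.1 applies to women in both arms, "Females should be using adequate contraceptive measures, should not be breast feeding", and gives no duration after the last dose.

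**The concern.** The stated hazard belongs to both drugs, while the stated post-dose safeguard for women belongs to one. The protocol gives no reason why the precaution should end with the last dose of sunitinib but continue for a month after savolitinib. A site that works from the protocol alone would tell a woman on savolitinib to continue for a month and would have nothing to tell a woman on sunitinib.

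What is at stake is possible foetal exposure shortly after the last sunitinib dose. Closed recruitment does not remove the issue: section 4.3.5 lets patients on either drug stay on treatment after the final analysis, so last doses still lie ahead.

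**Working it through.** The check is textual; the plan has no figure to reproduce.

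**Step 1. Rules for women, by arm**

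| Period | Savolitinib | Sunitinib |
|---|---|---|
| During treatment (3.6.1, Appendix D) | required | required |
| After last dose (3.6.1) | 1 month | not stated |
| After last dose (Appendix D, lead sentence) | at least 1 month | not stated |
| After last dose (Appendix D, abstinence bullet) | at least 1 month | not stated |

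**Step 2. Does another section fill the empty cells?**

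- Section 3.1, inclusion criterion 14: contraception and a negative pregnancy test, no post-dose duration.
- Section 5.2.5.1: the last scheduled pregnancy test is at treatment discontinuation.
- Sections 6.6 and 6.6.1: reporting of pregnancies, and stopping study drug if one occurs. Neither sets a contraception period.
- Section 6.8.2.1: the list of sunitinib risk-minimisation measures, from adrenal function to wound healing, has no pregnancy or contraception entry.
- Section 7.2.2: sunitinib dosing only.
- Section 6.4: cites the EU Summary of Product Characteristics (SPC) for sunitinib, but only to define expectedness of adverse events.
- Section 4.3.5: cites the national sunitinib label, but only for monitoring after the final analysis.

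None of these sets a period, and none defers to the label for one. Tests and reporting detect a pregnancy; they do not prevent exposure.

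**Step 3. How many women could be affected?**

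The synopsis expects about 50 patients, randomised 1:1, so the sunitinib arm has about 50 × 1/2 = 25. The protocol does not give the number of women of child-bearing potential. Assumptions, not from the protocol: 20% to 40% of patients are women, and 10% to 30% of those women are of child-bearing potential.

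- Low: 25 × 0.20 × 0.10 = 0.5
- High: 25 × 0.40 × 0.30 = 3.0

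Section 1.1.1 says that renal cell carcinoma is more common in men and usually occurs between 50 and 70 years of age, which points to the low end.

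**The case against.** The strongest defence is that the silence may be deliberate. Sunitinib is a marketed comparator, and a sponsor may set rules for its own drug and leave the comparator to its label. Under section 7.1 the commercial carton carries the patient leaflet, and in the US sites dispense locally sourced drug. The leaflet's content is not shown, and the consent pages are not in the public document, so either may give the instruction. This part stands: the gap can be claimed only for the visible protocol text. It does not close the gap, because the protocol nowhere says that it defers to the label on contraception. The leaflet is described as English-language, while section 5.3.1.4 names Italy, France and South Korea among the countries where one questionnaire is given.

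It also stands that the protocol does not show whether sunitinib needs a post-dose period, or how long. Section 3.6.1 speaks of foetal harm in general and says nothing about risk after the last sunitinib dose.

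A reader might go further in two ways that the document does not support:

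- **Women on sunitinib are the one sex-and-arm group left out.** For men, inclusion criterion 15 does run "during the study and for 6 months following discontinuation of study drug", and the condom rule in 3.6.1, "Therefore, male patients must use a condom during sexual intercourse with a female partner of childbearing potential", names no arm. But 3.6.1 rests that rule on savolitinib sperm findings. Sections 6.6.2 and 6.8.1.5 and Appendix D tie the men's 6 months to savolitinib, as does section 6.6 for reporting partner pregnancies. On that reading men on sunitinib have no period either, so a count of groups proves nothing.
- **The protocol already accepts a month of foetal risk after either drug, because section 4.3.5 collects pregnancies for 30 (±7) days after treatment.** That window covers serious adverse events, overdose and pregnancy together. It is the general safety follow-up and not a judgement on foetal risk.

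**Conclusion.** The point holds as a minor patient-safety gap. The protocol gives one reason for contraception that covers both drugs, then writes a post-dose rule for women that covers one, in three places, with no cross-reference for the other. The comparison is 1 month against nothing stated. It does not depend on how the men's wording is read.

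The reach is small: about 0.5 to 3 women in the sunitinib arm, on the assumed shares above, with the low end more likely. Contraception on treatment, pregnancy tests up to discontinuation and pregnancy reporting already apply to them.

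The conclusion rests on the visible text. It does not show that women on sunitinib are left uninformed, since the leaflet or consent form may inform them, nor that 1 month is the right length for sunitinib.

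**What to change.** Extend the women's post-dose wording from savolitinib to both study drugs in section 3.6.1 and in both places in Appendix D (lead sentence and abstinence bullet). Set the period at 1 month or more for either drug and, for sunitinib, at the period in its EU SPC if that is longer. Section 6.4 already names that document as the reference for sunitinib. Notify sites so that women still on sunitinib are told before their last dose.

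The cost is a wording change in three places in a protocol amendment and a letter to sites, with no extra visits or tests. The downside is a short additional contraception period for very few women, which may prove unnecessary because the document does not establish what sunitinib requires.

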Appendix E Actions Required in Cases of Increases in Liver Biochemistry and Evaluation of Hy's Law

Introduction

This Appendix describes the process to be followed in order to identify and appropriately report potential Hy's Law (PHL) cases and Hy's Law (HL) cases. It is not intended to be a comprehensive guide to the management of elevated liver biochemistries. Specific guidance on the management of liver abnormalities can be found in Section 6.8.1.2 of the protocol.

During the course of the study the Investigator will remain vigilant for increases in liver biochemistry. The investigator is responsible for determining whether a patient meets PHL criteria at any point during the study.

All sources of laboratory data are appropriate for the determination of PHL and HL events. These include samples taken at scheduled study visits and other visits including central and all local laboratory evaluations, even if collected outside of the study visits. For example, PHL criteria could be met by an elevated ALT from a central laboratory **and/or** elevated TBL from a local laboratory.

The Investigator will also review adverse event (AE) data (for example, for AEs that may indicate elevations in liver biochemistry) for possible PHL events.

The Investigator will participate, together with AstraZeneca clinical project representatives, in review and assessment of cases meeting PHL criteria to agree whether HL criteria are met. HL criteria are met if there is no alternative explanation for the elevations in liver biochemistry other than Drug Induced Liver Injury (DILI) caused by the Investigational Medicinal Product (IMP).

The Investigator is responsible for recording data pertaining to PHL/HL cases and for reporting AEs and Serious Adverse Events (SAEs) according to the outcome of the review and assessment in line with standard safety reporting processes.

Definitions

Potential Hy's Law (PHL)

Aspartate Aminotransferase (AST) or Alanine Aminotransferase (ALT) $\geq 3x$ Upper Limit of Normal (ULN) **together with** Total Bilirubin (TBL) $\geq 2x$ ULN at any point during the study following the start of study medication irrespective of an increase in Alkaline Phosphatase (ALP).

Hy's Law (HL)

AST or ALT $\geq 3xULN$ **together with** TBL $\geq 2xULN$, where no other reason, other than the IMP, can be found to explain the combination of increases, eg, elevated ALP indicating cholestasis, viral hepatitis, another drug.

For PHL and HL the elevation in transaminases must precede or be coincident with (ie, on the same day) the elevation in TBL, but there is no specified timeframe within which the elevations in transaminases and TBL must occur.

Identification of potential Hy's Law cases

In order to identify cases of PHL it is important to perform a comprehensive review of laboratory data for any patient who meets any of the following identification criteria in isolation or in combination:

- ALT $\geq 3xULN$
- AST $\geq 3xULN$
- TBL $\geq 2xULN$

The Investigator will without delay review each new laboratory report and if the identification criteria are met will:

- Notify the AstraZeneca representative.
- Determine whether the patient meets PHL criteria (see Definitions within this Appendix for definition) by reviewing laboratory reports from all previous visits.
- Promptly enter the laboratory data into the laboratory eCRF.

Follow-up:

Potential Hy's Law criteria not met

If the patient does not meet PHL criteria the Investigator will:

- Inform the AstraZeneca representative that the patient has not met PHL criteria.
- Perform follow-up on subsequent laboratory results according to the guidance provided in the Clinical Study Protocol.

Potential Hy's Law criteria met

If the patient does meet PHL criteria the Investigator will:

- Notify the AstraZeneca representative who will then inform the central Study Team.

- Within 1 day of PHL criteria being met, the Investigator will report the case as an SAE of PHL; serious criteria 'Important medical event' and causality assessment 'yes/related' according to CSP process for SAE reporting.
- For patients that met PHL criteria prior to starting IMP, the Investigator is not required to submit a PHL SAE unless there is a significant change* in the patient's condition.

The AstraZeneca Study Physician contacts the Investigator, to provide guidance, discuss and agree an approach for the study patients' follow-up (including any further laboratory testing) and the continuous review of data. Subsequent to this contact the Investigator will:

- Monitor the patient until liver biochemistry parameters and appropriate clinical symptoms and signs return to normal or baseline levels, or as long as medically indicated.
- Complete the follow-up SAE form as required.
- Investigate the aetiology of the event and perform diagnostic investigations as discussed with the AstraZeneca Study Physician.
- Complete the three Liver eCRF Modules as information becomes available.

Review and assessment of potential Hy's Law cases

The instructions in this Section should be followed for all cases where PHL criteria are met.

As soon as possible after the biochemistry abnormality was initially detected, the AstraZeneca Study Physician contacts the Investigator in order to review available data and agree on whether there is an alternative explanation for meeting PHL criteria other than DILI caused by the IMP, to ensure timely analysis and reporting to health authorities within 15 calendar days from the date that the PHL criteria were met. The AstraZeneca Global Clinical Lead (or equivalent) and Global Safety Physician will also be involved in this review together with other subject matter experts as appropriate.

According to the outcome of the review and assessment, the Investigator will follow the instructions below.

Where there is an agreed alternative explanation for the ALT or AST and TBL elevations, a determination of whether the alternative explanation is an AE will be made and subsequently whether the AE meets the criteria for a SAE:

- If the alternative explanation is **not** an AE, record the alternative explanation on the appropriate eCRF.
- If the alternative explanation is an AE/SAE, update the previously-submitted PHL SAE and AE eCRFs accordingly with the new information (reassessing event term, causality and seriousness criteria) following the AZ standard processes.

If it is agreed that there is **no** explanation that would explain the ALT or AST and TBL elevations other than the IMP:

- Send updated SAE (report term ‘Hy’s Law’) according to AstraZeneca standard processes.
 - The ‘Medically Important’ serious criterion should be used if no other serious criteria apply.
 - As there is no alternative explanation for the HL case, a causality assessment of ‘related’ should be assigned.

If, there is an unavoidable delay, of over 15 calendar days in obtaining the information necessary to assess whether or not the case meets the criteria for HL, then it is assumed that there is no alternative explanation until such time as an informed decision can be made:

- Provide any further update to the previously-submitted SAE of ‘Potential Hy’s Law’ (report term now ‘Hy’s Law case’) ensuring causality assessment is related to IMP and seriousness criteria is medically important, according to CSP process for SAE reporting.
- Continue follow-up and review according to agreed plan. Once the necessary supplementary information is obtained, repeat the review and assessment to determine whether HL criteria are still met. Update the previously-submitted PHL SAE report following CSP process for SAE reporting, according to the outcome of the review and amending the reported term if an alternative explanation for the liver biochemistry elevations is determined.

Actions Required for Repeat Episodes of Potential Hy’s Law

This section is applicable when a patient meets PHL criteria on study treatment and has already met PHL criteria at a previous on study treatment visit.

The requirement to conduct follow-up, review and assessment of a repeat occurrence(s) of PHL is based on the nature of the alternative cause identified for the previous occurrence.

The investigator should determine the cause for the previous occurrence of PHL criteria being met and answer the following question:

Was the alternative cause for the previous occurrence of PHL criteria being met found to be the disease under study eg, chronic or progressing malignant disease, severe infection or liver disease?

If No: follow the process for reporting PHL as an SAE, described in “Potential Hy’s Law criteria met” of this Appendix.

If Yes:

Determine if there has been a significant change in the patient’s condition* compared with when PHL criteria were previously met:

- If there is no significant change no action is required.
- If there is a significant change, follow the process for reporting PHL as an SAE, described in “Potential Hy’s Law criteria met” of this Appendix.

* A ‘significant’ change in the patient’s condition refers to a clinically relevant change in any of the individual liver biochemistry parameters (ALT, AST or total bilirubin) in isolation or in combination, or a clinically relevant change in associated symptoms. The determination of whether there has been a significant change will be at the discretion of the Investigator; this may be in consultation with the AstraZeneca Study Physician if there is any uncertainty.

References

FDA Guidance for Industry (issued July 2009) ‘Drug-induced liver injury: Premarketing clinical evaluation’:

<http://www.fda.gov/downloads/Drugs/GuidanceComplianceRegulatoryInformation/Guidances/UCM174090.pdf>

Appendix F Guidance for Evaluation of Objective Tumour Response Using RECIST 1.1 Criteria (Response Evaluation Criteria in Solid Tumours)

F 1 INTRODUCTION

This appendix details the implementation of RECIST 1.1 Guidelines (Eisenhauer et al 2009) for the D5082C00003 study with regards to Investigator assessment of tumour burden including protocol-specific requirements for this study.

F 2 DEFINITION OF MEASURABLE, NON-MEASURABLE, TARGET AND NON-TARGET LESIONS

Patients with at least one lesion (measurable and/or non-measurable) that can be accurately assessed at baseline by CT/MRI and is suitable for repeated assessment will be entered in this study.

Measurable:

A lesion, not previously irradiated, that can be accurately measured at baseline as ≥ 10 mm in the longest diameter (except lymph nodes which must have short axis ≥ 15 mm) with computed tomography (CT) or magnetic resonance imaging (MRI) and which is suitable for accurate repeated measurements.

Non-measurable:

- 1 All other lesions, including small lesions (longest diameter < 10 mm or pathological lymph nodes with ≥ 10 to < 15 mm short axis at baseline*).
- 2 Truly non-measurable lesions include the following: bone lesions, leptomeningeal disease, ascites, pleural / pericardial effusion, inflammatory breast disease, lymphangitic involvement of skin or lung, abdominal masses/abdominal organomegaly identified by physical examination that is not measurable by CT or MRI.
- 3 Previously irradiated lesions.**
- 4 Skin lesions assessed by clinical examination.
- 5 Brain metastases.

* Nodes with < 10 mm short axis are considered non-pathological and should not be recorded or followed as NTL.

**Localised post-radiation changes, which affect lesion sizes, may occur. Therefore, lesions that have been previously irradiated will not be considered measurable and must be selected as Non-Target Lesions (NTL) at baseline and followed up as part of the NTL assessment.

Special Cases:

Lytic bone lesions or mixed lytic–blastic lesions, with identifiable soft tissue components, can be considered measurable if the soft tissue component meets the definition of measurability. Blastic lesions are considered non-measurable.

Cystic metastases can be considered measurable lesions if they meet the criteria for measurability from a radiological point of view, but if non-cystic lesions are present in the same patient; these should be selected as target lesions.

Target lesions:

A maximum of 5 measurable lesions (with a maximum of 2 lesions per organ), representative of all lesions involved suitable for accurate repeated measurement, should be identified as target lesions (TL) at baseline.

Non-Target lesions:

All other lesions (or sites of disease) not recorded as TL should be identified as NTL at baseline.

F 3 METHODS OF ASSESSMENT

The same method of assessment and the same technique should be used to characterise each identified and recorded lesion at baseline and during follow-up visits.

A summary of the methods to be used for RECIST assessment is provided below and those excluded from tumour assessments for this study are highlighted, with the rationale provided.

Table F1 Summary of Methods of Assessment

Target lesions	Non-target lesions	New lesions
CT(preferred)	CT (preferred)	CT (preferred)
MRI	MRI	MRI
	Clinical Examination	Clinical Examination
	X-ray, Chest x-ray	X-ray, Chest x-ray
		Ultrasound
		Bone scan
		FDG-PET

F 3.1 CT and MRI

CT and MRI are generally considered to be the best currently available and reproducible methods to measure TL selected for response assessment and to assess NTL and identification of any new lesions.

In the D5082C00003 study it is recommended that CT examinations of the chest*, abdomen and pelvis will be used to assess tumour burden at baseline and follow-up visits. CT examination with intravenous (i.v.) contrast media administration is the preferred method. MRI should be used where CT is not feasible or it is medically contra-indicated. For brain lesion assessment, MRI is the preferred method.

- 1 *Chest, abdomen and pelvis CT/MRI scans should be performed at baseline.
- 2 *In those patients with thoracic lesions or upper abdomen lymphadenopathy identified at baseline assessment, chest, abdomen and pelvis should be performed at follow-up.
- 3 *In those patient with no disease present in the chest and no upper abdomen lymphadenopathy then follow-up is by abdomen and pelvis only.

F 3.2 Clinical examination

Clinical examination will not be used for assessment of TL. Clinically detected lesions can be selected as target lesions if they are assessed by CT or MRI scans. Clinical examination can be used to assess NTL and to identify the presence of new lesions.

F 3.3 X-ray

Chest X-ray

Chest X-ray assessment will not be used for assessment of TL as they will be assessed by CT examination or MRI examination. Chest X-ray can, however, be used to assess NTL and to identify the presence of new lesions.

Plain X-ray

Plain X-ray may be used as a method of assessment for bone NTL and to identify the presence of new bone lesions.

F 3.4 Ultrasound

Ultrasound examination will not be used for assessment of TL and NTL as it is not a reproducible method, does not provide an accurate assessment of tumour size and it is subjective and operator dependent. Ultrasound examination can, however, be used to identify the presence of new lesions. If new clinical symptoms occur and an ultrasound is performed then new lesions should be confirmed by CT or MRI examination.

F 3.5 Endoscopy and laparoscopy

Endoscopy and laparoscopy will not be used for tumour assessments, as they are not validated in the context of tumour assessment.

F 3.6 Tumour markers

Tumour markers will not be used.

F 3.7 Cytology and histology

Histology will not be used as part of the tumour response assessment as per RECIST 1.1.

Cytological confirmation of the neoplastic origin of any effusion that appears or worsens during treatment is required when the measurable tumour has met criteria for response or stable disease. In such circumstances, the cytology is necessary to differentiate between response / stable disease (an effusion may be a side effect of the treatment) and progressive disease (if the neoplastic origin of the fluid is confirmed). Where cytology findings are not available, any effusion that significantly worsens (from trace to large) or appearance of clinically significant effusion (requiring change in drug therapy) during the study treatment will be considered to be progression of NTL, or disease progression due to new lesions.

F 3.8 Isotopic bone scan

Bone lesions identified on an isotopic bone scan at baseline and confirmed by CT, MRI or X-ray at baseline should be recorded as NTL and followed by the same method as per baseline assessment.

Isotopic bone scans may be used as a method of assessment to identify the presence of new bone lesions at follow-up visits. New lesions will be recorded where a positive hot-spot that was not present on the baseline bone scan assessment is identified on a bone scan performed at any time during the study. The Investigator should consider the positive hot-spot to be a significant new site of malignant disease and represent true disease progression in order to record the new lesion. Confirmation by CT, MRI and x-ray is recommended where bone scan findings are equivocal.

F 3.9 FDG-PET scan

FDG-PET scans may be used as a method for identifying new lesions, according with the following algorithm: New lesions will be recorded where there is positive FDG uptake* not present on baseline FDG-PET scan or in a location corresponding to a new lesion on CT/MRI at the same follow-up visit. If there is no baseline FDG-PET scan available, and no evidence of new lesions on CT/MRI scans then follow-up CT/MRI assessments should be continued, scheduled as per protocol or clinical indicated, in order to confirm new lesions.

* A positive FDG-PET scan lesion should be reported only when an uptake greater than twice that of the surrounding tissue is observed.

F 4 TUMOUR RESPONSE EVALUATION

F 4.1 Schedule of evaluation

Baseline assessments should encompass all areas of known predilection for metastases in the disease under evaluation and should additionally investigate areas that may be involved based on signs and symptoms of individual patients and should be performed no more than 28 days before randomisation, and ideally should be performed as close as possible to the start of study treatment. Follow-up assessments will be performed every 6 weeks at the start of each cycle (± 7 days), for the first year, then every 12 weeks (± 1 week) relative to the date of randomisation, until objective disease progression as defined by RECIST 1.1. See Table 1 Study Schedule from Study Protocol for further information. Any other sites at which new disease is suspected should also be adequately imaged at follow-up.

If an unscheduled assessment was performed and the patient has not progressed, every attempt should be made to perform the subsequent assessments at their scheduled visits. This schedule is to be followed in order to minimise any unintentional bias caused by some patients being assessed at a different frequency than other patients.

F 4.2 Target lesions (TL)

F 4.2.1 Documentation of target lesions

A maximum of 5 measurable lesions, with a maximum of 2 lesions per organ (including lymph nodes), representative of all lesions involved should be identified as TL at baseline. Target lesions should be selected on the basis of their size (longest diameter for non-nodal lesions or short axis for nodal lesions), but in addition should be those that lend themselves to reproducible repeated measurements. It may be the case that, on occasion, the largest lesion does not lend itself to reproducible measurement in which circumstance the next largest lesion, which can be measured reproducibly, should be selected. The site and location of each TL should be documented as well as the longest diameter for non-nodal lesions (or short axis for lymph nodes). All measurements should be recorded in millimetres. At baseline the sum of the diameters for all TL will be calculated and reported as the baseline sum of diameters. At follow-up visits the sum of diameters for all TL will be calculated and reported as the follow-up sum of diameters.

Special cases:

- 1 For TL measurable in 2 or 3 dimensions, always report the longest diameter. For pathological lymph nodes measurable in 2 or 3 dimensions, always report the short axis. If the CT/MRI slice thickness used is >5 mm, the minimum size of measurable disease at baseline should be twice the slice thickness of the baseline scan.
- 2 If a lesion has completely disappeared, the longest diameter should be recorded as 0 mm.
- 3 If a TL splits into two or more parts, then record the sum of the diameters of those parts.

- 4 If two or more TL merge then the sum of the diameters of the combined lesion should be recorded for one of the lesions and 0 mm recorded for the other lesion(s).
- 5 If a TL is believed to be present and is faintly seen but too small to measure, a default value of 5 mm should be assigned. If an accurate measure can be given, this should be recorded, even if it is below 5mm.
- 6 If a TL cannot be measured accurately due to it being too large, provide an estimate of the size of the lesion.
- 7 When a TL has had any intervention eg, radiotherapy, embolisation, surgery etc., during the study, the size of the TL should still be provided where possible.

F 4.2.2 Evaluation of target lesions

This section provides the definitions of the criteria used to determine objective tumour visit response for TL.

Table F2 Evaluation of target lesions

Complete Response (CR)	Disappearance of all target lesions since baseline. Any pathological lymph nodes selected as target lesions must have a reduction in short axis to <10 mm.
Partial Response (PR)	At least a 30% decrease in the sum of the diameters of TL, taking as reference the baseline sum of diameters
Stable Disease (SD)	Neither sufficient shrinkage to qualify for PR nor sufficient increase to qualify for PD
Progressive Disease (PD)	At least a 20% increase in the sum of diameters of target lesions, taking as reference the smallest sum on study (this includes the baseline sum if that is the smallest on study). In addition to the relative increase of 20%, the sum must also demonstrate an absolute increase of at least 5mm.
Not Evaluable (NE)	Only relevant if any of the target lesions were not assessed or not evaluable or had a lesion intervention at this visit. Note: If the sum of diameters meets the progressive disease criteria, progressive disease overrides not evaluable as a target lesion response

F 4.3 Non-target lesions (NTL)

F 4.3.1 Evaluation of non-target lesions

All other lesions (or sites of disease) not recorded as TL should be identified as NTL at baseline. Measurements are not required for these lesions, but their status should be followed at subsequent visits. At each visit an overall assessment of the NTL response should be recorded by the Investigator. This section provides the definitions of the criteria used to determine and record overall response for NTL at the investigational site at each visit.

Table F3 Evaluation of non-target lesions

Complete Response (CR)	Disappearance of all non-target lesions since baseline. All lymph nodes must be non-pathological in size (<10 mm short axis).
Non-CR/Non PD	Persistence of one or more NTL
Progression (PD)	Unequivocal progression of existing non-target lesions. Unequivocal progression may be due to an important progression in one lesion only or in several lesions. In all cases the progression MUST be clinically significant for the physician to consider changing (or stopping) therapy.
Not Evaluable (NE)	Only relevant when one or, some of the non-target lesions were not assessed and, in the Investigator's opinion, they are not able to provide an evaluable overall non-target lesion assessment at this visit.

Note: For patients without target lesions at baseline, this is relevant if any of the non-target lesions were not assessed at this visit and the progression criteria have not been met.

To achieve ‘unequivocal progression’ on the basis of non-target lesions, there must be overall level of substantial worsening in non-target disease such that, even in presence of SD or PR in target lesions, the overall tumour burden has increased sufficiently to merit discontinuation of therapy. A modest ‘increase’ in the size of one or more non-target lesions is usually not sufficient to qualify for unequivocal progression status.

F 4.4 New lesions

Details of any new lesions will also be recorded with the date of assessment. The presence of one or more new lesions is assessed as progression.

A lesion identified at a follow up assessment in an anatomical location that was not scanned at baseline is considered a new lesion and will indicate disease progression.

The finding of a new lesion should be unequivocal: ie, not attributable to differences in scanning technique, change in imaging modality or findings thought to represent something other than tumour.

If a new lesion is equivocal, for example because of its small size, the treatment and tumour assessments should be continued until the new lesion has been confirmed. If repeat scans confirm there is a new lesion, then the progression date should be declared using the date of the initial scan.

F 4.5 Symptomatic deterioration

Symptomatic deterioration is not a descriptor of an objective response: it is a reason for stopping study therapy. Patients with ‘symptomatic deterioration’ requiring discontinuation of treatment without objective evidence of disease progression at that time should continue to undergo tumour assessments where possible until objective disease progression is observed.

F 4.6 Evaluation of Overall Visit Response

The overall visit response will be derived using the algorithm shown in Table F4.

Table F4 Overall Visit Response

Target lesions	Non-target lesions	New lesions	Overall response
CR	CR	No	CR
CR	NA	No	CR
NA	CR	No	CR
CR	Non CR / Non PD	No	PR
CR	NE	No	PR
PR	Non PD or NE	No	PR
SD	Non PD nor NE	No	SD
NA	Non CR / Non PD	No	SD (Non CR / Non PD)
NE	Non PD or NE	No	NE
NA	NE	No	NE
PD	Any	Yes or No	PD
Any	PD	Yes or No	PD
Any	Any	Yes	PD

CR = Complete Response, PR = Partial Response, SD = Stable Disease, PD = Progressive Disease, NE = not evaluable, NA = not applicable (only if relevant if there were no TL/NTL at baseline)

F 5 CENTRAL REVIEW

